## 2 Statistical Analysis Plan Statements

### 2.1 Compliance with Good Clinical Practice

This Statistical Analysis Plan is designed to comply with the standards issued by the International Council for Harmonisation of Technical Requirements for Pharmaceuticals for Human Use (ICH) (E3: Structure and Content of Clinical Study Reports, E6: Good Clinical Practice, and E9: Statistical Principles for Clinical Trials).

### 3 List of Abbreviations

AD	Atopic dermatitis
ADA	Anti-drug antibodies
ADaM	Analysis data model
AE	Adverse event
AESI	Adverse event of special interest
ATC	Anatomical Therapeutic Chemical
CI	Confidence interval
CMH	Cochran-Mantel-Haenszel
CRF	Case Report Form
CSA	Cyclosporine A
CTR	Clinical trial report
DLQI	Dermatology Life Quality Index
EASI	Eczema Area and Severity Index
EASI50	At least 50% reduction in EASI score
EASI75	At least 75% reduction in EASI score
EASI90	At least 90% reduction in EASI score
ECG	Electrocardiogram
EQ-5D-5L	EuroQoL 5-Dimension Health Questionnaire 5 Level
FAS	Full analysis set
FDA	US. Food and Drug Administration
GCP	Good Clinical Practice
HADS	Hospital Anxiety and Depression Scale
ICH	The International Council for Harmonisation of Technical Requirements for Pharmaceuticals for Human Use
IGA	Investigator's Global Assessment
IMP	Investigational medicinal product
LOCF	Last observation carried forward
MAR	Missing at random
MedDRA	Medical Dictionary for Regulatory Activities
MI	Multiple imputation

nAB	Neutralising antibodies
NRS	Numeric rating scale
POEM	Patient Oriented Eczema Measure
PT	Preferred term
Q2W	Every 2 weeks
QC	Quality control
SAP	Statistical Analysis Plan
SAE	Serious adverse event
SCORAD	Scoring Atopic Dermatitis
SF-36	36-Item Short Form Health Survey
TCS	Topical corticosteroid
SOC	System Organ Class
VAS	Visual analogue scale

## 4 Introduction

The statistical analysis will be performed as outlined in the Clinical Trial Protocol. This Statistical Analysis Plan (SAP), prepared before the unblinding of the trial, contains a more technical and detailed elaboration of relevant points in the statistical analysis described in the Clinical Trial Protocol.

### Change log of major changes or additions to the protocol, made in this SAP:

1. Major eligibility criteria have been defined and a review of all critical protocol deviations has been formalised in accordance with ICH E9 and the protocol. From these, it will be possible to make exclusions to the full analysis set during a blind review of data.
2. Further specification to the analyses of the primary and secondary endpoints, where applicable, in relation to when there is not enough data to facilitate MI of data using Rubin's rule and the handling of such situations.

## 5 Trial analysis sets

As specified in the protocol, but with some further specification of the full analysis set (FAS).

The FAS will, as specified in protocol, consist of all subjects randomised and dosed with IMP. But, in addition to this, exclusions can be made in accordance ICH E9 if major eligibility criteria have been breached or a critical protocol deviation has been identified to seriously impact data integrity in relation to the primary endpoint of this trial. These major eligibility criteria are inclusion criteria 3, 6, 7, 8, and 12, as defined in the protocol. These are selected due to their criticality in relation to defining the targeted population.

During the blind review of data each critical protocol deviation and any violation of the defined major eligibility criteria will be reviewed, and a decision will be made whether the subject will be removed from or kept in the FAS.

In the analysis set definition document, made prior to unblinding of the trial, documentation of any exclusions will be made and each critical protocol deviation will have a reason for excluding or not excluding the subject from the FAS.

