7.2 Number of subjects needed

Assuming a screening failure rate of 25%, approximately 333 subjects will be screened and approximately 250 subjects will be randomly assigned 1:1 to tralokinumab 300 mg+TCS or placebo+TCS. Randomisation will be handled using the interactive response technology (IRT) to ensure continued blinding in the trial.

The statistical power considerations for this sample size are described in Section 14.1.

This trial will be conducted at approximately 40 sites in Europe. The anticipated minimum number of randomised subjects per trial site is 4 and the maximum number of subjects per trial site is 30.

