14.1 Sample size

With a significance level of 5%, a sample size of 250 subjects will provide 99% power for detecting a treatment difference for the primary endpoint, assuming an EASI75 response rate at Week 16 of 40% vs 15% for tralokinumab+TCS and placebo+TCS, respectively. Assuming a response rate of 30% vs 15% in reduction of Worst Daily Pruritus NRS (weekly average) score of at least 4 from baseline to Week 16 for tralokinumab+TCS and placebo+TCS, respectively, the trial will provide at least 80% power for rejecting the hypotheses related to the primary endpoint and the secondary endpoint evaluating pruritus at Week 16.

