14.2 Trial analysis sets

All screened subjects will be accounted for in the CTR.

All subjects randomised to treatment and exposed to the IMP will be included in the full analysis set (FAS) and will be analysed for efficacy. Exclusions from the FAS can be considered in special cases as described in the ICH E9 guideline, Section 5.2.1 (37). If it is decided to exclude a randomised subject from the FAS, a justification addressing ICH E9 will be given.

The following safety analysis sets are applied:

- ‘safety analysis set’ for all subjects exposed to IMP within the treatment period.
- ‘safety follow-up analysis set’ for all subjects exposed to IMP within the safety follow-up period.

The decisions regarding inclusion/exclusion of subjects from the trial analysis sets will be documented in the analysis set definition document before breaking the randomisation code.

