14.3.16 General principles

Unless otherwise stated, all significance tests will be 2-sided using the 5% significance level. All CIs will be presented with 95% degree of confidence. An observed-cases approach will be used for tabulations of data by visit (i.e. involving only those subjects who attended each specific visit).

Categorical data will be summarised using the number and percentage of subjects in each category and treatment group. Continuous data will be summarised using the mean, median, standard deviation, 1st quartile, 3rd quartile, minimum, and maximum values.

All the analyses specified in the protocol will be reviewed in relation to the blinded data actually obtained and the statistical analysis plan and the analysis set definition document will be finalised before breaking the randomisation code.

Any changes from the statistical analysis planned in this clinical trial protocol will be described and justified in a protocol amendment, the statistical analysis plan, and/or in the CTR dependent on the type of deviation.

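### SAP Section 5 allows case-by-case removal from the FAS for an undefined critical protocol deviation, without limiting it to pre-randomisation events or giving Panel 13 precedence

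*SAP*

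**What the plan says.** Protocol Section 14.2 sets the starting point: "All subjects randomised to treatment and exposed to the IMP will be included in the full analysis set (FAS"). It then allows exclusions in special cases under ICH E9, with a justification for each.

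SAP Section 5 keeps that definition and names two grounds for exclusion:

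- **Eligibility:** breach of inclusion criteria 3, 6, 7, 8 or 12. This is a closed list about status at or before randomisation.
- **Deviation:** cases where "a critical protocol deviation has been identified to seriously impact data integrity in relation to the primary endpoint of this trial". There is no list and no limit on when the deviation occurred.

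For each critical deviation or eligibility breach, "a decision will be made whether the subject will be removed from or kept in the FAS". This happens during a blind review. Exclusions are recorded in the analysis set definition document before unblinding, and every critical deviation carries a reason for excluding or keeping the subject.

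Other sections bear on the point:

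- Protocol Appendix 3D has the sponsor assess deviations but does not define critical.
- Protocol Section 14.3.4 treats deviations in IMP administration as protocol deviations.
- Protocol Section 14.3.8 bases all analyses of the primary endpoint on the FAS.
- Protocol Section 14.3.8.1 and Panel 13 already assign an outcome to rescue treatment, permanent discontinuation and missing data.

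**The concern.** The eligibility ground depends on facts settled before treatment could act, so applying it uniformly need not disturb the comparison between arms. The deviation ground is different. As written, it can take in events after randomisation, such as dosing deviations or use of prohibited medication, and these can follow from how well the disease is controlled. Their frequency, and the outcomes of the subjects who have them, can then differ by arm. Concealing the arm from the reviewers stops deliberate selection. It does not balance a process that treatment itself drives.

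The route also overlaps with the estimand. Higher-potency TCS and systemic agents are prohibited medication in Protocol Section 9.7, and when given as rescue they make the subject a non-responder under Section 9.5 and Panel 13. The plan does not say which rule wins. The same subject could be a non-responder in the denominator or be absent from it.

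No analysis of all randomised and dosed subjects without exclusions is specified, so a reader of the report could not see what any exclusions had done to the result.

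**Working it through.** **Inputs**

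- Level: "all significance tests will be 2-sided using the 5% significance level" (Protocol 14.3.16).
- Size and power: "a sample size of 250 subjects will provide 99% power for detecting a treatment difference for the primary endpoint" (Protocol 14.1).
- Planning rates for the primary endpoint: 40% on tralokinumab and 15% on placebo (same section).
- Pruritus: "Assuming a response rate of 30% vs 15% in reduction of Worst Daily Pruritus NRS (weekly average) score of at least 4" (Protocol 14.1), with at least 80% power for this endpoint and the primary together.
- Allocation: 1:1 (Protocol 7.2), so n = 125 per arm.
- Number of exclusions: not given. The values below are assumptions, from 0 to 10 subjects in one arm, or 0 to 10% of each arm.

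**Step 1. Reproduce the plan's power**

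Power = Φ{[|p1 − p2|√n − 1.96√(2p̄(1 − p̄))] / √(p1(1 − p1) + p2(1 − p2))}, where p̄ is the mean of the two rates.

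- EASI75, p̄ = 0.275: (0.25 × 11.180 − 1.96 × 0.6315) / 0.6062 = 2.57, so power is 99.5%. The stated 99% reproduces.
- Pruritus, p̄ = 0.225: (0.15 × 11.180 − 1.96 × 0.5906) / 0.5810 = 0.894, so power is 81.4%. The product 0.995 × 0.814 = 0.810 agrees with at least 80%.

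**Step 2. Balanced exclusions**

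| Excluded per arm | EASI75 power | Pruritus power |
|---|---|---|
| 0% | 99.5% | 81.4% |
| 2% | 99.4% | 80.7% |
| 5% | 99.3% | 79.4% |
| 10% | 99.0% | 77.2% |

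Loss of power is immaterial for the primary endpoint. For pruritus the margin over 80% is thin and is gone at 5%.

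**Step 3. Unbalanced exclusions, five non-responders from one arm (assumed)**

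In whole subjects, the planning rates are 50/125 = 40.0% and 19/125 = 15.2%, a difference of 24.8 points.

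- From tralokinumab only: 50/120 = 41.7%; 41.7 − 15.2 = 26.5 points (+1.7).
- From placebo only: 19/120 = 15.8%; 40.0 − 15.8 = 24.2 points (−0.6).

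**Step 4. Other counts**

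With exactly 40% and 15% (50 and 18.75 expected responders, 25.0 points), removing m non-responders gives 50/(125 − m) − 0.15 for tralokinumab, or 0.40 − 18.75/(125 − m) for placebo.

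| m | From tralokinumab only | From placebo only |
|---|---|---|
| 2 | 25.7 | 24.8 |
| 6 | 27.0 | 24.2 |
| 10 | 28.5 | 23.7 |

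**Step 5. Worst case for a false claim**

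Suppose there is no true effect and all m removals are tralokinumab non-responders. Two binomials of 125 were enumerated exactly with an unstratified pooled z test. The table shows the chance of a significant result favouring tralokinumab (nominal 2.5%).

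| m | Response 15% in both arms | Response 40% in both arms |
|---|---|---|
| 0 | 2.4% | 2.4% |
| 2 | 2.9% | 3.1% |
| 6 | 3.8% | 5.3% |
| 10 | 4.7% | 8.8% |

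**The case against.** The SAP does not invent FAS exclusion. The protocol already allows it in special cases with a justification, and the SAP describes itself as formalising that. Exclusion is a possibility and not a rule. It needs a serious impact on data integrity for the primary endpoint, is decided blind, needs a written reason either way, and is fixed before unblinding. Most of the events one would worry about already have an outcome under Panel 13, and SAP Section 6.8.5 says intercurrent events and missing values are handled as in the protocol. With few exclusions the shift is small.

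All of that stands, and it rules out several stronger readings that a reader might reach:

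- *That the SAP undoes the randomised comparison.* The text opens a discretionary route with safeguards; it does not direct that anyone be removed.
- *That the SAP excludes subjects for post-randomisation events.* It is silent on timing. It fails to rule such exclusions out, which is a narrower point.
- *That decisions are made with outcomes in view.* Protocol Section 14.3.16 mentions review against blinded data, but SAP Section 5 does not say what the reviewers see.
- *That the bias favours tralokinumab.* Lack-of-effect events would be expected more often on placebo if the drug works, and removing placebo non-responders shrinks the difference.
- *That the shift could be 3.5 points, by removing five placebo responders (19/125 = 15.2% to 14/120 = 11.7%).* Deviations driven by poor disease control do not select responders, and an arm-blinded reviewer could not target them.

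The objection leaves four gaps open: critical is undefined, timing is unrestricted, precedence of Panel 13 is unstated, and no analysis without exclusions is planned.

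**Conclusion.** The concern holds as a gap in the exclusion rule. SAP Section 5 permits exclusions that could depend on treatment, and blind review alone cannot ensure that these are balanced. The direction of any bias is not determined by the documents.

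On the assumption of five non-responders from one arm, a 24.8-point difference moves to about 26.5 or about 24.2 points, and primary power stays near 99%. Marked inflation of the false-positive rate needs about ten removals, all non-responders and all from tralokinumab. Nothing in the documents suggests that pattern. Every size here rests on assumed counts and the planning response rates. The false-positive figures also use an unstratified test in place of the planned Mantel-Haenszel analysis. The content of ICH E9 was not used.

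This is worth correcting before unblinding because it decides who is in the primary analysis and costs little. It is not evidence that the primary comparison is invalid.

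**What to change.** Amend SAP Section 5 before unblinding:

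1. Limit FAS exclusion to breaches of inclusion criteria 3, 6, 7, 8 or 12, judged only on pre-randomisation data and applied by one rule to every violator.
2. Keep all other randomised, dosed subjects in the FAS, and state that Panel 13 governs events after randomisation.
3. Define a critical deviation, and move exclusions on that ground to a supplementary sensitivity analysis.
4. If any subject is excluded from the FAS, also report EASI75 at Week 16 in all randomised and dosed subjects, with exclusions and reasons tabulated by arm.

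The cost is about a paragraph of SAP text and one extra analysis. The downside is that a few subjects with poor-quality data stay in the primary analysis.

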## 6 Statistical analysis

### 6.1 Aspects related to the COVID-19 pandemic

As specified in the protocol. Technical aspects of attributing events and missing data to the COVID-19 pandemic is further detailed in Section 6.8.8.

### 6.2 Disposition

Subject disposition will be summarised as detailed in the protocol.

Additionally, reasons for not attending the nominal Week 16 and Week 26 visits will be summarised for randomised subjects. Not attending the nominal Week 16 and Week 26 visits due to the COVID-19 pandemic will be added to the list of reasons based on the information documented in the eCRF. Technical aspects of attributing missed visits to the COVID-19 pandemic is further detailed in Section 6.8.8.

The number of randomised subjects and screen failures will be summarised for all screened subjects. Screen failures will be summarised by reason as well as overall.

For the safety follow-up visit, attendance will be summarised for all subjects included in the safety follow-up analysis set. Not attending the safety follow-up visit due to the COVID-19

Trial ID: LP0162-1346	Date: 21-OCT-2020	Version: v1.0 Page 10 of 35
-----------------------	-------------------	--------------------------------

pandemic will be added to the list of reasons, as for reasons for not attending the nominal Week 16 and Week 26 visits.

### **6.3 Demographics and baseline characteristics**

Demographics and baseline characteristics will be summarised as specified in the protocol.

Duration of AD in years will be calculated as (age at Week 0) minus (age at onset of AD).

The table of concomitant medication at baseline will include medication with start date before or at the Week 0 visit date which does not have an end date before the Week 0 visit date. For handling of incomplete dates, see Section 6.8.3.

In addition, any concomitant medication taken during the treatment period will be summarised.

In case a subject has been randomised based on a wrong value of a stratification variable, the correct value of the variable will always be used in descriptive statistics and analyses. Subject(s) who were randomised within a wrong stratum will be listed.

### **6.4 Exposure and treatment compliance**

#### **6.4.1 Compliance**

Compliance will be summarised and listed. Technical aspects of attributing missed IMP doses to the COVID-19 pandemic are further detailed in Section 6.8.8.

#### **6.4.2 Exposure**

Exposure time will be summarised as detailed in the protocol with the exception that it will be presented using years of exposure instead of days. Definitions used for exposure time during the treatment period is detailed in Section 6.8.2.

### **6.5 Rescue treatment**

Presentation of rescue treatment and the definition of rescue treatment is as defined in the protocol.

For the presentation of rescue treatment up until the Week 16 visit (actual or nominal) the planned date of the Week 16 visit will be used if no Week 16 visit exists (actual or nominal).

Due to the allowance of TCS in the screening period, some subjects might during this period use TCS of a high enough potency to be categorised as rescue treatment ending on the day of randomisation. Such cases will not be categorised as rescue medication as the assumption will be that the use of high potency TCS will stop prior to administration of IMP.

The global start date of the COVID-19 pandemic is defined in Section [6.8.2](#).

## 6.6 Analysis of efficacy

As described in Section 6.3, in case a subject is randomised based on a wrong value of a stratification variable, the correct value of the variable will always be used in the analysis to reflect the actual characteristics of the subject. The variable collected at randomisation will be used.

### 6.6.1 Intercurrent events

As specified in the protocol. The timing and technical handling of intercurrent events in relation to analysed visits and the technical aspects of attributing events and missing data to the COVID-19 pandemic are further detailed in Sections 6.8.5, 6.8.6 and 6.8.8.

### 6.6.2 Analysis of the primary endpoint (EASI75 at week 16)

The analysis of the primary endpoint will be as specified in the protocol, further changes or specifications to the analysis of the endpoint are described here.

#### Primary analysis of the primary estimand ('COVID-19 modified composite')

In case not enough data is missing due to the COVID-19 pandemic or set to missing due to subject-onset of the COVID-19 pandemic (less than 2 imputed values within treatment groups), the primary analysis of the secondary estimand (composite) will be used instead, as it will not be possible to estimate the variance using Rubin's rule for MI.

#### Primary analysis of the tertiary estimand ('treatment policy')

As stated in the protocol, it is expected that the number of observed values in the 2 treatment groups of discontinued subjects is too small to facilitate MI of data using Rubin's rule. In this case, the primary analysis will be substituted with the sensitivity analysis. A limit of 2 or less observed values within each of the treatment groups of discontinued subjects will be used to enforce when the sensitivity analysis will become the primary analysis.

#### Sensitivity analysis of the tertiary estimand ('treatment policy')

For the 2 treatment groups within the discontinued subjects, in case not enough data (less than 2 data points) is missing due to the COVID-19 pandemic or set to missing due to subject-onset of the COVID-19 pandemic, the sensitivity analysis will assume any missing data to be non-response, as it will not be possible to estimate the variance using Rubin's rule for MI.

## 6.6.3 Analysis of secondary endpoints

### 6.6.3.1 Binary secondary endpoints

The analysis of the binary secondary endpoints will be as specified in the protocol and section 6.6.2, further changes or specifications for endpoints' analyses are described here.

Multiple imputation is further specified in section 6.6.4.

#### Calculation of Weekly average of Worst Daily pruritus NRS

The weekly average will only be calculated if at least 4 out the 7 weekly assessments are available and otherwise set to missing. In case of several entries on the same day the worst observation on that day is used.

The baseline value of the Worst Daily Pruritus NRS (weekly average) will be calculated as defined in the protocol based on daily assessments of the 7 days preceding randomisation including day of randomisation (day -6 to 0 where day 0 is the day of randomisation).

For the treatment period, the Worst Daily Pruritus NRS (weekly average) for Week 1 will be calculated based on scores recorded on day 1 to day 7 (where day 0 is the day of the first dose). Similarly, for week 2 to week 25, the weekly average for week x will be calculated based on scores recorded on day  $7*x-6$  to day  $7*x$  (where day 0 is the day of first dose).

Since the Week 26 visit (regular or nominal) may occur between day 179 and day 185, the week 26 weekly average will instead be based on the 7 days before (and including) the day of the week 26 visit (regular or nominal). In case no week 26 visit (regular or nominal) exists, the date of an unscheduled visit or early termination visit can be mapped as per Section 6.8.4 (if existing), else the planned date will be used.

#### Sensitivity analyses of the primary estimand of IGA 0/1 and reduction of Worst Daily Pruritus NRS (weekly average) of at least 4 at Week 16 and 26

The tipping-point analyses are not considered relevant for secondary endpoints, thus the sensitivity analyses of the primary estimand of IGA 0/1 and reduction of Worst Daily Pruritus NRS (weekly average) of at least 4 at Weeks 16 and 26 will not be done.

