14.3.5 Rescue treatment

Rescue treatment will be defined by the following algorithm:

Concomitant medications with ‘Dermatitis atopic’ or ‘Dermatitis infected’ as the preferred term (PT) for the indication, and either of the following:

- ATC2 code H02
- Preferred name Methotrexate, Methotrexate sodium, Ciclosporin, Azathioprine, Mycophenolate-mofetil, Mycophenolate-acid, Mycophenolate-sodium, Dupilumab, Crisaborole, or Alitretinoin
- ATC4 code D07AD or D07BD or D07CD or D07XD
- Confirmed rescue treatment (by investigator) in reported term for the indication, and ATC4 code D07AB or D07BB or D07CB or D07XB or D07AC or D07BC or D07CC or D07XC

As described in Section 9.5, investigators should make every attempt to conduct efficacy and safety assessments immediately before administering any rescue treatment. Therefore, if rescue treatment has start date the same day as an efficacy assessment, then it is assumed that the assessment is not influenced by rescue treatment.

Rescue treatment will be summarised for the entire treatment period as well as for the period up until the Week 16 visit (actual or nominal). Rescue treatment will also be summarised for the periods prior to and after the start of the COVID-19 pandemic, within the treatment period. The start date(s) of the COVID-19 pandemic will be decided prior to unblinding in the statistical analysis plan, possibly reflecting on when trial procedures were disrupted on a national level.

Additionally, rescue treatment will be summarised for the entire treatment period by the variables: prior CSA use (yes/no), country (Germany: yes/no), and baseline disease severity (IGA 3 or 4).

A summary table of rescue treatment by type (topical and systemic) and by overall group (corticosteroids, immunosuppressants, and other) will be made for the entire treatment period as well as for the period up until the Week 16 visit (actual or nominal).

[figure not shown]
In addition, the time to first use of rescue treatment will be presented using Kaplan-Meier plots for the whole treatment period.

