### 6.8.6 Timing of intercurrent events

Actions taken based on intercurrent events will be dependent on whether or not an intercurrent event happens prior to a relevant visit. The rule will be that if any regarded intercurrent event happens prior to the date of the visit then the intercurrent event will be defined to be prior to the relevant visit. The following list of dates will be used in a prioritised manner as the date of the visit, i.e. if a date higher in the hierarchy exists that date will be used:

1. Observed date of the visit. When no data is available from the scheduled visit, data and visit date can be mapped to the visit per the rules stated in Section 6.8.4.
2. Planned date of the visit – 7 days, to account for the visit window.

In case intercurrent events occurs on the same date the following prioritise list will be used: rescue treatment, permanent discontinuation of IMP, and then subject-onset of the COVID-19 pandemic.

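### The Week 16 diary average covers fixed days 106–112, but intercurrent events are dated against the site visit, so post-rescue diary days can count as response without rescue; few subjects are likely to be affected

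*SAP*

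**What the plan says.** **Diary week.** For Worst Daily Pruritus NRS, SAP 6.6.3.1 states: "Similarly, for week 2 to week 25, the weekly average for week x will be calculated based on scores recorded on day". The range given is 7x−6 to 7x, counted from first dose. Eczema-related Sleep NRS follows the same rules (SAP 6.6.5). An average needs enough entries: "The weekly average will only be calculated if at least 4 out the 7 weekly assessments are available and otherwise set to missing". Week 26 is handled differently: "the week 26 weekly average will instead be based on the 7 days before (and including) the day of the week 26 visit". The reason given is that this visit can fall anywhere on days 179–185.

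**Order of events.** SAP 6.8.6 sets the order by date: "if any regarded intercurrent event happens prior to the date of the visit then the intercurrent event will be defined to be prior". The date that counts is the observed visit date, or that of a mapped early termination or unscheduled visit. If neither exists, it is the planned date minus 7 days.

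**Same-day rescue.** Protocol 14.3.5 treats a same-day assessment as unaffected: "if rescue treatment has start date the same day as an efficacy assessment, then it is assumed that the assessment is not influenced".

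**Estimand.** Protocol 14.3.8.1 defines response as obtained without starting rescue or permanently stopping IMP, and codes non-response when either happens before the Week 16 visit. Protocol 14.3.9 applies this to an itch reduction of at least 4. The diary is completed each morning about the past 24 hours (protocol 11.3.4.2).

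**The concern.** EASI and IGA are scored on the visit day, before any rescue given that day, so dating events against the visit suits them. A diary average covers a week, and at Week 16 that week does not move with the visit. After an early visit it runs on, and rescue started at or after the visit is not prior even though the remaining diary days follow it. The same-day assumption in protocol 14.3.5 cannot cover those later days.

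Itch reduction at Week 16 is a secondary endpoint tested in the hierarchy (protocol 14.3.6) and the second endpoint in the power statement (protocol 14.1). At stake is whether a subject whose itch fell after rescue can be counted as having responded without it.

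**Working it through.** **Inputs.** The diary-week formula and the Week 26 visit days are from SAP 6.6.3.1; the ±3-day visit window from protocol Panel 2; the event rule and the no-visit date from SAP 6.8.6; the mapping window of days 7x−6 to 7x+7 from SAP 6.8.4, Table 8; 250 subjects randomised 1:1, so 125 per arm, from protocol 14.1 and 7.2.

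**The plan's own figures.** 7 × 26 ± 3 gives days 179–185, as the SAP states. A normal-approximation power calculation with 125 per arm gives 0.995 for 40% vs 15% (stated 99%) and 0.814 for 30% vs 15%. Their product, treating the endpoints as independent, is 0.810 (stated at least 80%).

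**Week 16 days.** Diary week: 7 × 16 − 6 = 106 to 7 × 16 = 112. Visit: 112 ± 3 = 109 to 115. Date used if there is no visit: 112 − 7 = 105. Mapped visit: 106 to 119.

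**Mismatches.** Rescue on day r is prior only if r is earlier than the visit day. Because the diary is a morning entry, a diary day is post-rescue if it is later than r.

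| Visit day | Rescue day not counted as prior → post-rescue days in the average | Rescue day counted as prior, with no post-rescue day in the average |
|---|---|---|
| 109 | 109 → 3; 110 → 2; 111 → 1 | none |
| 110 | 110 → 2; 111 → 1 | none |
| 111 | 111 → 1 | none |
| 112 | none | none |
| 113 | none | 112 |
| 114 | none | 112, 113 |
| 115 | none | 112, 113, 114 |
| No visit (105) | 105 → 7, falling by one a day to 111 → 1 | none |

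A mapped visit on day 106 with rescue that day leaves 6 post-rescue days.

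**Effect on a score.** If k of the 7 days are each 4 points lower, the mean falls by 4k/7: 0.57 for one day, 1.71 for three, 4.0 for seven. As a deliberately strong illustration, take baseline 8.5, four days at 6 and three post-rescue days at 2. The mean is (4 × 6 + 3 × 2)/7 = 4.29 and the reduction 4.21, a responder. With all days at 6 the reduction is 2.5, a non-responder.

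**How many subjects.** The documents give no rescue rate. Assume that 10–40% use rescue, spread evenly over 112 days, and that visits fall evenly on days 109–115. The mean number of rescue days in the middle column is (3 + 2 + 1 + 0 + 0 + 0 + 0)/7 = 0.857. Exposed subjects per arm are 125 × 0.10 × 0.857/112 = 0.096, up to 125 × 0.40 × 0.857/112 = 0.383. If 5–15% have no Week 16 visit, this adds 125 × 0.10 × 0.05 × 7/112 = 0.04 to 125 × 0.40 × 0.15 × 7/112 = 0.47 per arm. One subject whose status did change would move an arm's rate by 1/125 = 0.8 percentage points.

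**With the diary week ended on the visit day.** The same listing gives no mismatch in either column for any visit day from 109 to 115.

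**The case against.** - **Late visits.** A reader might infer that the right-hand column is also misclassification: a rescue-free diary week coded as non-response. The documents do not support that. Protocol 14.3.8.1 codes rescue before the Week 16 visit as non-response, and 14.3.9 carries the rule to itch. This is a misalignment, not an error.
- **Direction of bias.** It is tempting to say that the rule favours the arm with more rescue. Late-visit coding works against that same arm, about equally often under the assumptions above, so no net direction is shown.
- **Week 26 as precedent.** The diary stops at Week 26, so a fixed week could lose entries after an early visit. The SAP cites visit timing, not intercurrent events. The difference therefore does not prove an oversight at Week 16, but it does show that a visit-anchored week is workable.
- **Ambiguity.** Odd-numbered diary weeks have no visit, yet protocol 14.3.11 asks for analyses by visit or week, so the cut-off for diary weeks is not fully defined. If diary weeks were held to have no visit date, day 105 would always apply, which widens the gap. Protocol 14.3.8.1 also excludes data captured after rescue when the imputed data sets are built, which could be read as dropping diary days. SAP 6.8.5 and Table 9, however, select data by visit, and no rule removes single days from an average.
- **Discontinuation.** Panel 3 has the diary continue after IMP is stopped, while protocol 14.3.10 expects it to be returned. How far the problem extends to discontinuation therefore depends on reconciling the two.

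**Conclusion.** The mismatch stands, in one direction. For visits on days 109–111, and more so with no visit, the stated rules let post-rescue diary days count towards response defined as free of rescue. This is a low-severity defect of definition in a hierarchy-tested endpoint. It is unlikely to decide the result.

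Under the assumed rescue rates, about 0.1–0.4 subjects per arm with an in-window visit are exposed (at most about 0.3 percentage points, 0.383/125), and a further 0.04–0.5 per arm if 5–15% miss the visit. Exposed does not mean changed: a responder status flips only if the fall in itch is quick and large enough to cross the threshold. Rescue clustered on visit days would raise these counts. A reader might infer that several subjects per arm change status, but nothing in the documents supports such a figure.

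**What to change.** In SAP 6.6.3.1, base the Week 16 weekly averages of pruritus and sleep NRS on the 7 days up to and including the observed or mapped Week 16 visit, as already specified for Week 26. Because the diary is a morning entry, rescue given at the visit then falls after the last entry used.

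In SAP 6.8.6, add a rule for diary endpoints when no visit exists: keep days 106–112 and judge intercurrent events against the last day of that week (day 112), not the planned date minus 7. Anchoring alone would leave the largest gap open. Week 26 needs the same rule, since without a visit its diary week ends on the planned date while the event cut-off is 7 days earlier.

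The cost is a few sentences and a derivation change before unblinding. The downside is overlap with an adjacent weekly average in by-week displays, and possibly in the imputation covariates. It is at most 3 days for an in-window visit: a day-109 visit uses days 103–109 and shares 103–105 with Week 15; a day-115 visit shares 113–115 with Week 17. A mapped visit can share more: 6 days at day 106 and all 7 at day 119.
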